6.4.1.9. Work Productivity and Activity Impairment Questionnaire

The generic version of the WPAI:general health (GH) ([Appendix J](#)) questionnaire measures the overall effect of health on productivity at work and daily activities. The specific health problems version of the WPAI questionnaire allows investigators to attribute productivity and activity impairment issues to specific health conditions.

After the employment status of a respondent is identified, 3 open-ended questions are asked concerning (1) hours absent from work due to health problems (or specific condition), (2) hours absent from work due to other reasons, and (3) hours actually worked. Two additional questions are included that ask about the impact of health on productivity, 1 concerning productivity at

work and the other concerning daily activities outside of work. The response format of each item of the WPAI questionnaire consists of an 11-point scale ranging from 0 (no impairment) to 10 (complete impairment) (Reilly et al 1993).

The following scores will be derived based on the WPAI: GH questionnaire. Multiply scores by 100 to express in percentages.

- Percent work item missed due to health: $\frac{Q2}{Q2+Q4}$
- Percent impairment while working due to health: $\frac{Q5}{10}$
- Percent overall work impairment due to health: $\frac{Q2}{Q2+Q4} + \left[\left(1 - \frac{Q2}{Q2+Q4} \right) \times \frac{Q5}{10} \right]$
- Percent activity impairment due to health: $\frac{Q6}{10}$

Patients will complete the WPAI questionnaire at time points specified in [Table 1](#) and [Table 2](#).

6.4.2. Efficacy Analysis

No statistical testing will be applied on the exploratory efficacy analysis.

6.4.2.1. Electronic Headache Diary Data

The exploratory variables listed below will be summarized by visit/month. The summary statistics of the change from baseline and 95% confidence interval of the means will be presented.

- total number of migraine days
- total headache days of at least moderate severity
- total headache days of any severity
- total number of days of use of any acute headache medication
- total number of headache hours of at least moderate severity
- total number of headache hours of any severity
- total number of days with nausea or vomiting
- total number of days with photophobia and phonophobia

The means \pm SEs of monthly change from baseline values of number of migraine days, headache days of at least moderate severity, headache days of any severity, and days of use of any acute headache medication will be plotted by month for each treatment group.

The number (%) of patients who reach at least 50%, 75%, and total (100%) reduction in the number of migraine days (and headache days of at least moderate severity) during the 4-week period after visits 2, 3, 4, 7, and 13 will be presented by visits/months. The 95% confidence interval of the responder rate by normal approximation will be presented.

The number (%) of patients who reach at least 50%, 75%, and total (100%) reduction in the number of migraine days (and headache days of at least moderate severity) during the 4-week

period after visits 4 and sustain the same level of response during the 4 week periods after visits 7 and 13 will be presented by visits/months.

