2. STUDY DESIGN

2.1. General Design and Study Schema

This is an approximately 19-month, multicenter, randomized, double-blind, parallel-group study to evaluate the long-term safety, tolerability, and efficacy of sc TEV-48125 in adult patients with migraine. For patients who complete the pivotal efficacy studies of TEV-48125 (Studies TV48125-CNS-30049 and TV48125-CNS-30050), the study will consist of a 12-month treatment period and a 6.5-month follow-up period. For patients who have not participated in a pivotal efficacy study, the study will consist of a screening visit and 28-day run-in period, a 12-month treatment period, and a 6.5-month follow-up period.

Female and male patients 18 to 70 years of age, inclusive, with CM and EM who complete the pivotal efficacy studies (Studies TV48125-CNS-30049 and TV48125-CNS-30050) and approximately 300 patients (approximately half of whom have a diagnosis of CM and half of whom have a diagnosis of EM) who have not participated in the pivotal efficacy studies may enter this long-term safety, tolerability, and efficacy study if they meet the inclusion/exclusion criteria and provide informed consent. In addition, patients who do not complete the pivotal efficacy studies and those patients who complete the pivotal efficacy studies but do not wish to continue treatment during this long-term safety, tolerability, and efficacy study may attend a follow-up visit during this study for the purpose of ADA assessment approximately 7.5 months after their last dose of study drug.

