2.3. Sample Size and Power Considerations

There are no statistical considerations for this sample size. A total of 1842 patients (867 patients from Study TV48125-CNS-30049, 675 patients from Study TV48125-30050, and approximately 300 patients who did not participate in the pivotal efficacy studies) are planned for enrollment, and a 30% drop-out rate is anticipated.

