2.4. Randomization and Blinding

2.4.1. Randomization

This is a randomized study with patients being stratified by gender, country, and preventive medication use at baseline (yes, no) during the pivotal efficacy studies or during this study if they are not rolling over from the pivotal efficacy study.

Patients rolling over from the pivotal efficacy studies who were randomized to the active treatment groups will continue receiving the same treatment throughout the study. Patients rolling over from the pivotal efficacy studies who received placebo and new patients will be randomly assigned in a 1:1 ratio to receive quarterly TEV-48125 at 675 mg or monthly TEV-48125 at 225 mg (Note: Patients with CM will receive a 675-mg loading dosing at visit 2 and TEV-48125 at 225 mg at each subsequent visit.).

Patient randomization codes will be maintained in a secure location within Teva Clinical Supply Chain. At the time of analysis, when treatment codes are needed, the Teva statistician assigned to the study will make a request to unblind and will receive the unblinded codes.

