6. EFFICACY ANALYSIS

6.1. General

The FAS will be used for all efficacy analyses. The patients with CM and patients with EM will be summarized separately for their efficacy endpoints. The descriptive statistics will be presented by treatment group and visits/months for new patients and placebo-treated rollover patients, TEV-48125-treated rollover patients, and overall under the same treatment, unless otherwise specified.

Efficacy endpoints will be derived from headache related question responses (eg, occurrence of headache, duration of headache in each day, maximum severity of headache, and acute migraine-specific medication use etc. [Appendix A](#)) collected daily using an electronic headache diary device for month 1, 2, 3, 6 and 12.

Following the Classification Committee of the International Headache Society guidelines ([Silberstein et al 2008](#)), headache days of at least moderate severity for both CM and EM patients will be defined for the purpose of this study as a calendar day (0:00 to 23:59) when the patient reports:

- a day with headache pain that lasts ≥ 4 hours with a peak severity of at least moderate severity
- or
- a day when the patient used an acute migraine-specific medication (triptans or ergots) to treat a headache of any severity or duration

Migraine day is endorsed based on the same criteria as described in the pivotal studies. For CM patients, a migraine day is endorsed when at least 1 of the following situations occur:

- a calendar day (0:00 to 23:59) demonstrating ≥ 4 consecutive hours of a headache meeting criteria for migraine with or without aura
- a calendar day (0:00 to 23:59) demonstrating ≥ 4 consecutive hours of a headache meeting criteria for probable migraine, a migraine subtype where only 1 migraine criterion is missing
- a calendar day (0:00 to 23:59) demonstrating a headache of any duration that was treated with migraine-specific medications (triptans and ergot compounds)

For EM patients, a migraine day is endorsed when at least 1 of the following situations occur:

- a calendar day (0:00 to 23:59) demonstrating ≥ 2 consecutive hours of a headache meeting criteria for migraine with or without aura
- a calendar day (0:00 to 23:59) demonstrating ≥ 2 consecutive hours of a headache meeting criteria for probable migraine, a migraine subtype where only 1 migraine criterion is missing

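### The normal-approximation intervals for responder rates cover less than 95% in cells with few responders and collapse to 0% (0%, 0%) with none; this could affect the 100% rows

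*SAP*

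**What the plan says.** SAP 6.4.2.1 tabulates, by month, the patients who reach "at least 50%, 75%, and total (100%) reduction in the number of migraine days", and does the same for headache days of at least moderate severity. The windows are months 1, 2, 3, 6 and 12. For these rates it states: "The 95% confidence interval of the responder rate by normal approximation will be presented". It gives no alternative for small counts or for zero responders. No interval is specified for the sustained-responder rows.

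The size of a table cell follows from SAP 6.1: "The patients with CM and patients with EM will be summarized separately for their efficacy endpoints", by treatment group, "for new patients and placebo-treated rollover patients, TEV-48125-treated rollover patients, and overall under the same treatment". SAP 6.4.1.1 counts early discontinuations as non-responders. SAP 4.4 and 6.4.2 rule out inferential analysis and testing.

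**The concern.** The textbook normal-approximation interval takes its standard error from the observed proportion. When that proportion is near zero the standard error is too small, and at zero it vanishes. The interval then covers less often than its label says, can run below 0%, and at zero responders claims perfect precision.

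The 100% rows are the natural place for this. New CM patients must show at least 15 headache days and at least 8 migraine days in the run-in (SAP 2.1), so a 100% migraine-day response means none at all in a 4-week window. Counting discontinuations as non-responders, where "a 30% drop-out rate is anticipated" (SAP 2.3), lowers late-month rates further. With no testing planned, the interval is the main statement of uncertainty printed with each rate. An interim report for the licence application is also planned (SAP 2.5.1).

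**Working it through.** **Inputs from the documents.** SAP 2.3: "A total of 1842 patients (867 patients from Study TV48125-CNS-30049, 675 patients from Study TV48125-30050, and approximately 300 patients who did not participate". The parts add up: 867 + 675 + 300 = 1842. The new patients are "approximately half of whom have a diagnosis of CM and half of whom have a diagnosis of EM" (SAP 2.1), so about 150 each. Placebo rollovers and "new patients will be randomly assigned in a 1:1 ratio to receive quarterly TEV-48125 at 675 mg" or the monthly regimen (SAP 2.4.1). The plan has no precision target or expected responder rate to reproduce; the only stated figure to test is the nominal 95%.

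**Assumptions.** The pivotal studies allocated 1:1:1, all their patients roll over, and nearly all enter the full analysis set. None of this is stated.

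**Cell sizes per regimen.**
- Former active patients: CM 867/3 = 289; EM 675/3 = 225.
- New plus former placebo: CM (289 + 150)/2 = 219.5, about 220; EM (225 + 150)/2 = 187.5, about 188.
- Overall: CM 289 + 219.5, about 508; EM 225 + 187.5, about 412.

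**Formulas** (x responders of n, r = x/n, z = 1.96).
- Wald: r ± z·√(r(1−r)/n).
- Wilson: [r + z²/(2n) ± z·√(r(1−r)/n + z²/(4n²))] / (1 + z²/n).
- Exact coverage at true rate p: the sum of Binomial(n, p) probabilities over all x whose interval contains p. Because this oscillates with p, the table averages it over p ± 20%.

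**Average Wald coverage, by assumed true rate.**

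| n | 0.5% | 1% | 2% | 3% | 5% | 10% |
|---|---|---|---|---|---|---|
| 188 | 0.61 | 0.84 | 0.88 | 0.91 | 0.93 | 0.939 |
| 220 | 0.66 | 0.89 | 0.90 | 0.92 | 0.93 | 0.940 |
| 225 | 0.67 | 0.89 | 0.90 | 0.92 | 0.93 | 0.941 |
| 289 | 0.76 | 0.88 | 0.91 | 0.925 | 0.935 | 0.943 |
| 412 | 0.87 | 0.90 | 0.92 | 0.93 | 0.94 | 0.945 |
| 508 | 0.90 | 0.91 | 0.93 | 0.935 | 0.94 | 0.946 |

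At 20-30% it is 0.945-0.949 in every cell.

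**Where the shortfall starts.** Average coverage drops below 0.90 at about 4 or fewer expected responders: rates up to about 2.2% at n = 188 (188 × 0.022 = 4.1), 1.8% at 220-225, 1.4% at 289, 1.0% at 412 and 0.6% at 508. It drops below 0.93 at about 10 or fewer: up to about 5.4% at n = 188 (188 × 0.054 = 10.2), 3.4% at 289 and 1.8% at 508.

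**Limits outside the possible range.** The Wald lower limit is negative when x < z²(1 − x/n) = 3.84(1 − x/n), that is at 1, 2 or 3 responders in all these cells. At n = 188 the chance of this is 73% at p = 1%, 46% at 2% and 1.4% at 5%.

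**Zero responders.** The chance at n = 188 and p = 1% is 0.99^188 = 15%. Wald then gives (0%, 0%) whatever the cell size. For n = 188 the Clopper-Pearson upper limit is 1 − 0.025^(1/188) = 1.9%, and the Wilson upper limit is 3.84/(188 + 3.84) = 2.0%.

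**After the change.** Wilson average coverage is 0.949-0.962 in every cell for rates from 0.5% to 40%. Clopper-Pearson is never below 0.95 (0.951-0.995).

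**The case against.** The strongest objection is that the size rests on rates the documents do not give. That stands. At 3-5%, average coverage is about 0.91-0.94, a modest shortfall; figures far below 95% need about 4 or fewer expected responders in a cell.

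A reader might infer that some 75% rows are also well below nominal. The documents do not support this. At a 75%-responder rate of 7.5% or more, average coverage is about 0.94 in every SAP cell, and a large shortfall would need a rate of about 2% or less. Non-responder counting with 30% drop-out could take 5% down to 5% × 0.7 = 3.5%, but would not by itself put a 75% row in that region.

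A reader might also point to much smaller cells, such as new patients alone (150/2 = 75 per regimen within an indication), where coverage is far worse. Protocol 9.5.4 does separate new from rollover patients. SAP 6.1, however, pools new patients with former placebo patients, and the SAP preface says the SAP prevails. The SAP 6.4.3 subgroups cover mean change only. Incomplete rollover or an early data cut could shrink cells, but the documents do not say by how much.

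The intervals are also descriptive, and the count and percentage appear beside them, so a reader can see when a row rests on very few responders. That stands too and limits the consequence. Finally, for common responses the specified method is adequate, so there the change is mainly for uniformity.

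**Conclusion.** The point holds as a conditional, low-severity one. The specified interval under-covers in cells expecting fewer than about 5-10 responders, has a negative lower limit at 1-3 responders, and has zero width at none. The last two follow from the formula and need no assumed rate. How often they arise, and how far coverage falls, depends on responder rates that neither document gives. The 100% rows could be affected, but the documents do not show that they will be; the 75% rows are not shown to be affected.

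The calculations rest on reading the normal approximation as Wald, 1:1:1 pivotal allocation, full rollover and near-complete entry to the full analysis set. Smaller cells would raise the rate thresholds in proportion. No test, comparison or trial conclusion uses these limits.

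**What to change.** In SAP 6.4.2.1, specify the Wilson score method in place of the normal approximation for the responder-rate intervals. Clopper-Pearson is an acceptable alternative if guaranteed coverage is preferred; it is conservative and somewhat wider in general. Using one method for all three response levels keeps the tables uniform and loses nothing in the common-response rows.

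The cost is one SAP phrase and one software option. Data collection, trial conduct and the point estimates do not change; only the printed limits do. Making the change before the interim report would keep interim and final tables consistent.

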6.4.2.2. Patients Discontinuing Concomitant Preventive Medications during the Treatment Period

The proportion of patients discontinuing concomitant preventive medications during the treatment period for those who used concomitant preventive migraine medications will be summarized.

6.4.2.3. Six-Item Headache Impact Test

Summary of the HIT-6 total score will be presented for CM patients by their treatment group and visits/months. The summary and 95% confidence interval of the change from baseline will also be presented by visits/months.

6.4.2.4. Migraine Disability Assessment Questionnaire

The total MIDAS score and change from baseline score will be summarized for EM patients by their treatment group and visits/months. The 95% confidence interval of the change from baseline will also be presented.

The number (%) of patients in each disability grade will be summarized by visits/months.

6.4.2.5. Migraine-Specific Quality of Life Questionnaire

The transformed scores for the 3 domains (ie, Role Function-Restrictive, Role Function-Preventive and Emotional Function) and the rescaled raw dimension score of MSQOL will be summarized by visits/months. The 95% confidence interval of the change from baseline will also be presented.

6.4.2.6. EuroQol-5 Dimension Questionnaire

The number (%) of patients rating their scale of 1 to 5 for the 5 domains of EQ-5D-5L will be presented by visits/months. The VAS and the change from baseline with 95% confidence interval of the VAS will be summarized by visits/months.

6.4.2.7. Patient Global Impression of Change Scale

The number (%) of patients rating their scale of 1 to 7 of the change in the severity of illness following treatment and their dichotomous scale of “Yes” or “No” rated by PGIC assessments will be presented by visits/months.

6.4.2.8. Patient Health Questionnaire

The change from baseline in total PHQ-9 score and 95% confidence interval will be summarized by visits/months.

6.4.2.9. Work Productivity and Activity Impairment Questionnaire

For the patients who are currently employed, their scores of

- percent work item missed due to health

- percent impairment while working due to health
- percent overall work impairment due to health
- percent activity impairment due to health

will be summarized by visits/months.

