9.5.4.4. Exploratory Efficacy Analysis

All efficacy variables will be summarized descriptively. For continuous variables, descriptive statistics (n, mean, SD, standard error of mean, median, minimum, and maximum) will be provided for actual values and changes from baseline to each visit. For categorical variables, frequency and percentage will be provided. For rollover patients, their baseline is defined as the baseline in the pivotal efficacy studies.

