- proportion of patients discontinuing concomitant preventive medications during the treatment period
- mean change from baseline (day 0) in disability score in patients with CM, as measured by the HIT-6, at visits 8 and 14
- mean change from baseline (day 0) in disability score in patients with EM, as measured by the MIDAS questionnaire, at visits 8 and 14
- mean change from baseline (day 0) in quality of life, as measured by the MSQOL questionnaire, at visits 8 and 14
- mean change from baseline (day 0) in patient health status, as measured by the EQ-5D-5L questionnaire, at visits 8 and 14
- assessment of patient satisfaction, as measured by the PGIC scale at visits 3, 5, 8, 11, and 14
- mean change from baseline (day 0) in patient depression status, as measured by the PHQ-2 and PHQ-9, at visits 8 and 14
- mean change from baseline (day 0) in patient work productivity and activity impairment, as measured by the WPAI questionnaire, at visits 8 and 14

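### SAP 6.4.2.9 does not specify the change from baseline that defines the WPAI endpoint, and it limits activity impairment to employed patients (minor fix)

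*SAP*

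**What the plan says.** SAP 2.2.3 lists the endpoint as "mean change from baseline (day 0) in patient work productivity and activity impairment, as measured by the WPAI questionnaire, at visits 8 and 14". Protocol 2.3.3 and 9.5.3 define it the same way. For continuous efficacy variables, Protocol 9.5.4.4 adds that descriptive statistics "will be provided for actual values and changes from baseline to each visit".

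SAP 6.4.2.9 is the section that plans the WPAI output. It begins "For the patients who are currently employed, their scores of", lists four derived percentages (work time missed, impairment while working, overall work impairment, activity impairment) and states that they "will be summarized by visits/months". Nothing else is specified there.

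On employment, SAP 6.4.1.9 describes the questionnaire: "After the employment status of a respondent is identified, 3 open-ended questions are asked concerning" absence and hours worked. Two further questions cover productivity at work and daily activities outside work.

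The SAP preface gives the SAP precedence where the two documents differ. SAP 13 reports no changes to the protocol-specified analyses.

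**The concern.** The endpoint is a within-patient change, while the analysis section asks for a level at each visit. A programmer working from 6.4.2.9 alone would build a table of visit scores in employed patients and no change column. A reader of that table could get at change only by subtracting visit means.

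Those means need not come from the same patients. Employment is established inside the questionnaire, so the natural reading is that it is judged afresh at each completion, although the SAP does not say so. Patients who leave the study, lose work or find work would move in or out of the rows.

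The employed-only condition also covers all four scores, including one that a patient without a job can supply.

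**Working it through.** The plan states no WPAI figure to reproduce, so the check is mainly a comparison of texts.

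**1. Endpoint against analysis.** SAP 2.2.3 gives the statistic as mean change from baseline, at visits 8 and 14. SAP 6.4.2.9 gives scores by visit or month, in employed patients, with no change and no interval.

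**2. Is change implied by house style?** The other change-from-baseline endpoints are handled as follows:

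| Endpoint | SAP section | Change from baseline named | 95% CI named |
|---|---|---|---|
| Diary variables | 6.4.2.1 | yes | yes |
| HIT-6 | 6.4.2.3 | yes | yes |
| MIDAS | 6.4.2.4 | yes | yes |
| MSQOL | 6.4.2.5 | yes | yes |
| EQ-5D VAS | 6.4.2.6 | yes | yes |
| PHQ-9 | 6.4.2.8 | yes | yes |
| WPAI | 6.4.2.9 | no | no |

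The HIT-6 section, for example, says: "The summary and 95% confidence interval of the change from baseline will also be presented by visits/months". The PHQ section says: "The change from baseline in total PHQ-9 score and 95% confidence interval will be summarized by visits/months". The SAP names the change wherever it wants it, so silence on WPAI cannot safely be read as implying it.

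**3. Can the change be calculated?** Yes. SAP 4.2 defines a day-0 WPAI baseline, taken from the pivotal study for rollover patients. SAP 5.3 summarises that baseline. Tables 1 and 2 schedule the WPAI at visits 8 and 14.

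**4. What a difference in visit means contains.** Let S be the mean score of patients in the employed, observed set at both times, and suppose none of them changes. Let d be the share of the baseline set missing later, with baseline scores g points above S on average. Let e be the share of the later set that is new, with scores h points above S on average.

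- Baseline mean = (1 − d)·S + d·(S + g) = S + d·g
- Later mean = (1 − e)·S + e·(S + h) = S + e·h
- Later minus baseline = e·h − d·g

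The true within-patient change is zero by construction, so this remainder is composition only. It is zero when g = 0 and h = 0. The documents give none of d, e, g or h for employed patients, so its sign and size are open. A paired change in patients with both values has no such term.

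**5. Activity impairment.** SAP 6.4.1.9 derives this score from item 6 divided by 10, and the item concerns daily activities outside work. No employment item enters the formula. The restriction in 6.4.2.9 therefore drops non-employed patients from a score that they can provide.

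**The case against.** The strongest reply is that 6.4.2.9 is silent on change and does not remove it. SAP 6.4 refers to the endpoint list in 2.2.3, which still contains the WPAI change, and Protocol 9.5.4.4 still asks for changes from baseline. On that view the precedence rule is not triggered, and the entry in SAP 13 is consistent with an omission. This stands to the extent that a reader should not infer that the endpoint will not be produced. The documents support only that the section governing the output does not specify it.

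Four other stronger readings are tempting and are not supported.

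- **A bias of known size.** A reader might take the anticipated 30% drop-out as d, assume leavers start 10 points worse, and obtain 0.30 × 10 = 3.0 points. The gap is in neither document. The 30% refers to all patients and is not shown to be WPAI loss at visit 14. That visit doubles as the early-withdrawal visit, the WPAI is scheduled there, and withdrawing patients are to have its procedures (Protocol 3.1, 3.14.4.1, 4.4). SAP 4.6 excludes early-termination data from by-visit summaries for safety data only.
- **Different patients at each visit.** The sets could overlap heavily, and the SAP does not say at which visit employment is judged. Only some shift in membership can be expected.
- **A distorted treatment effect.** Protocol 3.9 calls the study uncontrolled, and SAP 4.4 and 6.4.2 plan no inference or testing.
- **Loss of the most impaired workers from the overall work score.** If item 2 is above zero and item 4 is zero, the formula gives 1 + 0 × (item 5)/10 = 100% for any recorded item 5. It fails only if item 5 is blank, and the form is not reproduced in the document available.

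It is also fair to object that requiring employment at both times conditions on a post-baseline event. A paired summary excludes people who lost work, possibly because of migraine. That limits how the result should be described, but it does not justify omitting the change.

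**Conclusion.** The point holds as an inconsistency within the SAP. The WPAI endpoint is a change from baseline, and 6.4.2.9, read literally, does not tabulate one. WPAI is the exception among the change endpoints compared above. Visit means are not a secure substitute, because their difference can include changes in who is employed and observed. No size can be given: it depends on quantities that the documents do not supply, and it may be zero. This part rests on reading employment status as assessed at each completion, which is natural but not stated.

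The employed-only limit on activity impairment follows directly from the text and needs no assumption.

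The consequence is small. This is one exploratory, descriptive endpoint in a study whose primary objective is safety and tolerability.

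**What to change.** In SAP 6.4.2.9:

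- Add change from baseline (n, mean, SD, 95% CI) for each WPAI score at visits 8 and 14, in patients with both values.
- For the three work scores, require employment at baseline and at the visit in question, and report those n.
- For percent activity impairment, use all patients with both values, whatever their employment status.
- Keep the visit scores as supporting output, and state the visit at which employment is judged for them.
- Add a note that the paired summary describes only patients who remain in the study and, for the work scores, in work.

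This brings 6.4.2.9 into line with SAP 2.2.3, Protocol 9.5.4.4 and the entry in SAP 13. The cost is a few lines of SAP text and one extra block in an existing table.
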